9.5.5 Analyses of Anticancer Activity

The following endpoints will be summarized to meet the study secondary objective of characterizing preliminary efficacy:

- ORR, defined as the proportion of patients with an objective tumor response (either partial response [PR] or complete response [CR] per Investigator using Response Evaluation Criteria in Solid Tumors version 1.1[RECIST v1.1]) in patients with measurable disease, including best radiographic response for soft tissue
- A reduction in PSA level by $\geq 50\%$
- Distribution of the best PSA response
- Time to SSE defined as symptomatic fracture, radiation or surgery to bone, or spinal cord compression

- rPFS defined as the time from the first dose of study treatment (CORT125281 and/or enzalutamide) to the date when the first site of disease is found to progress on CT, MRI, or radionucleotide bone scan per PCWG3, or death whichever occurs first. Progression will be assessed by the Investigator using RECIST v1.1. The proportion of patients who are progression-free at 4, 6, and 12 months will also be summarized.
- DOR, defined as the time from the first occurrence of a documented objective tumor response to the time of radiographic progression (per Investigator using RECIST v1.1) or death from any cause on study, whichever occurs first
- Time to PSA progression, clinical progression (per Investigator), and bone disease progression
- Overall survival, defined as the time from the first dose of study treatment (CORT125281 and/or enzalutamide) to the date of death from any cause

Data summaries will include number, percent and waterfall displays as appropriate. Time-to-event endpoints will be characterized using Kaplan-Meier method.

For the analyses of rPFS and DOR, data for the patients who have not experienced disease progression or death will be censored at the time of the last tumor assessment date.

Data for the analysis of overall survival will be censored at the time of the end of follow-up period. Dose adjustments/changes in enzalutamide will be summarized by CORT125281 dose and overall.

The change in markers of disease status, such as PSA and CTCs, will be compared between the Lead-In Period and Cycle 1, when possible.

These analyses will be performed in the Safety Population and Response-Evaluable Population.

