9.1. Secondary Efficacy Endpoints

Objective Response Rate (ORR): Patient listings of tumor response outcomes (CR, PR, non-CR/non-progressive disease, stable disease, progressive disease, unevaluable, or not assessed) at study visits, as well as best overall response per RECIST v1.1, will be presented by treatment regimen dose group and overall for the ITT population. By-group summary tables will include distribution of response outcomes, best overall response derived over all visits, and point estimates with Clopper-Pearson² 95% CIs for ORR, defined as the proportion of patients with an objective tumor response (either PR or CR) in patients with measurable disease, including best radiographic response for soft tissue.

For supportive purposes, best overall response and point estimates with Clopper-Pearson 95% CIs for ORR will also be summarized using confirmed response.

PSA Levels: PSA levels recorded at each visit will be listed. Proportions of patients in the Safety population who experience a 50% or greater reduction in PSA levels at any visit since baseline will be reported with Clopper-Pearson 95% CIs by treatment group and overall. Mean reduction levels will be characterized via summary statistics. Median time from date of first dose of exicorilant to PSA progression (first occurrence of 50% or greater increase in PSA levels), along with 95% CIs will be estimated via Kaplan-Meier method, and also plotted graphically by treatment group. Patients who are alive and progression-free will be censored at the date of their-last PSA evaluation.

In dose escalation and expansion phases separately, best PSA response will be illustrated graphically via waterfall plots. For each patient, the maximum percent change in PSA levels since baseline will be depicted on the response axis, with vertical bars below the baseline representing decline in the blood-based marker.

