Symptomatic Skeletal Event (SSE): SSE is defined as symptomatic fracture, radiation or surgery to bone, or spinal cord compression. SSEs include only symptomatic events of clear clinical significance. Kaplan-Meier estimates of median time from date of first dose of exicorilant to the first occurrence of SSE and associated 95% CIs, will be computed by treatment regimen dose group and overall for the Safety population. Patients who are event-free will be censored at the date of their end of study/treatment + 30 days visit. Kaplan-Meier graph of the probability of the event will also be constructed by treatment group.

Radiographic progression-free survival (rPFS): For the Response-Evaluable population, rPFS will be determined from the first dose of study treatment (exicorilant and/or enzalutamide) to the date when the first site of disease is found to progress on CT, MRI, or radionucleotide bone scan per PCWG3, or death, whichever occurs first. Progression will be assessed by the Investigator using RECIST v1.1.

$$\text{rPFS (months)} = (\text{earliest date of progression, death, or censoring} - \text{date of first study treatment} + 1) / 30.4375$$

Patients who do not experience disease progression or death (due to any cause) will be right-censored at the time of the last tumor assessment date. Censoring date will be based on the date patient was last known to be alive and progression-free (i.e., last assessment date) or data analysis cutoff date, whichever occurs first. Censoring rules are summarized in [Table 3](#) below.

Table 3: Censoring Rules for the Primary Analysis of PFS

Censoring Categories	Date of Censoring
Patients who did not have baseline or postbaseline tumor assessments and did not die on or before the data cutoff date	Date of first study treatment

Patients who did not have disease progression as determined by the Investigator and did not die on or before the data cutoff date	Date of the last adequate tumor assessment on or before the data cutoff date
Patients who did not have disease progression as determined by the Investigator on or before initiation of subsequent anticancer therapy for prostate cancer and did not die on or before the data cutoff date	Date of the last adequate tumor assessment on or before initiation of subsequent anticancer therapy and on or before the data cutoff date

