Patients who had 2 or more consecutive missed scheduled tumor assessments immediately prior to disease progression	Date of the last adequate tumor assessment without evidence of disease progression before the 2 missed tumor assessments and on or before the data cutoff date
Patients who did not have disease progression as determined by the Investigator and died more than 119 days from most recent tumor assessment.	Date of the last adequate tumor assessment on or before the data cutoff date

Note: If a patient meets the criteria for more than 1 censoring rule, PFS will be censored at the earliest censoring date.

Kaplan-Meier curves will be plotted by treatment regimen dose groups, and the estimate of median rPFS time (months) with 95% CI will be ascertained. For each cohort, progression-free rate at 4, 6, and 12 months will also be summarized.

Duration of response (DOR): Duration of response will be defined for patients in the Response-Evaluable population as the time from the first occurrence of a documented objective tumor response of CR or PR to the time of radiographic progression (per Investigator using RECIST v1.1) or death from any cause on study, whichever occurs first. Patients who have not experienced disease progression or death will be censored at the time of the last tumor assessment date. Date of censoring will be determined according to same rules as described for rPFS endpoint.

$$\text{DOR (months)} = (\text{earliest date of progression, death, or censoring} - \text{date of first documented objective response} + 1) / 30.4375$$

Kaplan-Meier graph will be plotted by treatment group and estimates of median duration with 95% CIs will be obtained for each dose cohort and overall. Patients who do not achieve a tumor response of CR or PR, will be excluded from this analysis.

Clinical progression: For the Response-Evaluable population, clinical disease progression, defined as time from first dose of study treatment (exicorilant and/or enzalutamide) to date of treatment discontinuation due to disease progression, will be estimated via the Kaplan-Meier

method. Patients who are alive and progression-free will be censored at their end of study visit. Median time to progression and associated 95% CIs will be summarized, overall and by treatment group. Kaplan-Meier graph of the probability of the event will also be plotted by treatment group.

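### SAP Table 3 censors rPFS at a switch to new therapy only for patients still alive at cutoff, so whether an event counts depends on a later death

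*SAP*

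**What the plan says.** Rows of Table 3 (SAP Section 9.1) are counted from the top.

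- **Row 3** covers patients without investigator-assessed progression "on or before initiation of subsequent anticancer therapy for prostate cancer and did not die on or before the data cutoff date". Their censoring date is "Date of the last adequate tumor assessment on or before initiation of subsequent anticancer therapy and on or before the data cutoff date".
- **Row 5** is the only row that censors a patient because of how he died: "Patients who did not have disease progression as determined by the Investigator and died more than 119 days from most recent tumor assessment". It uses the last adequate scan by cutoff, with no reference to a switch.
- **Note to the table:** "If a patient meets the criteria for more than 1 censoring rule, PFS will be censored at the earliest censoring date".
- **Protocol 9.5.5** has no switching rule for either rPFS or DOR; it states that "data for the patients who have not experienced disease progression or death will be censored at the time of the last tumor assessment date".
- **ORR (SAP 9.1)** is summarized with "best overall response derived over all visits".
- **DOR (SAP 9.1)** runs from the "date of first documented objective response", and "Date of censoring will be determined according to same rules as described for rPFS endpoint".

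Protocol 7.5 and 7.5.2 continue scans until progression when treatment stops for another reason, and record the dates of later therapies. Post-switch scans will therefore be in the database.

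**The concern.** A Kaplan-Meier censoring rule may use only what is known up to the censoring time. Row 3 also uses what happens afterwards. Switchers who stay alive leave the risk set at their last pre-switch scan. Switchers who die by cutoff stay in, and bring their post-switch progressions and deaths as events. Events are kept selectively among patients who do badly, which pulls the curve down. The same patient can also change from censored to event when the cutoff moves.

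At stake are the rPFS curve, its median, and the 4-, 6- and 12-month progression-free rates, which are named secondary summaries. DOR inherits the rule. ORR has no stated stop at a switch, so the two response endpoints can disagree about the same patient.

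**Working it through.** The plan states no figure that depends on this rule, so there is none to reproduce. The check applies Table 3 literally.

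**Inputs.** Scans every 8 weeks to week 24, then every 12 weeks (SAP Section 9): days 57, 113, 169, 253. Months = days / 30.4375 (SAP 9.1). Chosen for illustration: switch on day 120, cutoff on day 500. The last pre-switch scan is day 113, and 113 / 30.4375 = 3.71 months.

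**Step 1. Same history, different later death.**

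| After the switch | Fate | Result under Table 3 |
|---|---|---|
| Progression day 169 | Alive at cutoff | Row 3: censored, 3.71 months |
| Progression day 169 | Dies day 300 | Event, 169 / 30.4375 = 5.55 months |
| Progression day 169 | Dies day 501, one day after cutoff | Row 3: censored, 3.71 months |
| No progression, scans to day 253 | Alive at cutoff | Row 3: censored, 3.71 months |
| No progression, scans to day 253 | Dies day 300 (47 days after scan) | Event, 300 / 30.4375 = 9.86 months |
| No progression, scans to day 253 | Dies day 400 (147 days after scan) | Row 5: censored, 253 / 30.4375 = 8.31 months |

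Row 5 catches the last patient, but at a post-switch scan. The note on the earliest date chooses only among rules a patient meets, and a switcher who has died meets no switching rule. With the death condition removed from row 3, all six patients are censored at 3.71 months.

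**Step 2. DOR.** DOR = (end date − first response date + 1) / 30.4375. Take a patient alive at cutoff whose first PR is on the day-169 scan, after the switch. Row 3 puts his censoring date at day 113: (113 − 169 + 1) / 30.4375 = −55 / 30.4375 = −1.81 months. With a 12-week gap the result is (−84 + 1) / 30.4375 = −2.73 months.

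**Step 3. Size, by simulation.** All rates are assumptions: progression 10% per month, death 1% per month before and 5% after progression, switching independent of prognosis. The 8/12-week scans, last-scan censoring and row 5 are applied, with cutoff spread over 24-48 months. 12-month rPFS:

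| Switching per month | All events count, no switching rule | Row 3 for every switcher | Row 3 as written | Shortfall against consistent censoring |
|---|---|---|---|---|
| 5% | 29.2% | 29.1% | 27.5% | 1.6 points |
| 10% | 29.4% | 28.7% | 26.3% | 2.4 points |

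At 2% switching the shortfall is about 0.6 points.

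*Effect of cutoff.* A simpler model without scan timing or row 5 has a true value of 26.7%. As written, it gives 25.1% (5% switching) and 23.9% (10%) at 24-48 months, and as little as 24.3% and 21.5% at earlier cutoffs. The shortfall grows from 1.6 to 2.4 points and from 2.8 to 5.2 points.

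*Effect of the rates.* With median progression 5 months, median switch 4-12 months, median post-progression survival 6-12 months and one cutoff at day 730 (scans and row 5 applied), the shortfalls across four scenarios are 1.0-1.8 points at 4 months, 1.4-3.1 at 6 months and 2.5-5.5 at 12 months.

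**The case against.** **The size is modest and rests on assumptions.** This stands. Neither document gives a rate of switching before progression. Protocol 3.3.3 keeps patients on treatment through an isolated PSA rise, and row 3 does not concern anyone who progressed by the switch. Switching is still foreseeable: under Protocol 5.7.1.1, patients who had already progressed on enzalutamide stop it when CORT125281 is discontinued, so a stop for toxicity can end study treatment without radiographic progression.

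**The largest shifts need early cutoffs.** This stands too. Follow-up runs to two years after the last enrolment or to the end of radiographic follow-up, whichever is later (Protocol 3.1, 7.5), and the only planned interim analysis is for safety.

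**Little depends on it.** rPFS, ORR and DOR are secondary and descriptive (Protocol 9.3). Expansion sizing rests on PSA response, and the recommended dose on tolerability, PK and PD. This limits the severity but does not make the rule correct.

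**The repaired rule may depart from the protocol definition just as far.** In the simulation it does not: it lies 0.1 and 0.7 points below the all-events figure, against 1.7 and 3.1 for the text as written. That closeness depends on switching being unrelated to prognosis, so the fix should not be said to recover the truth.

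**The death condition may be wording carried over from rows 1 and 2.** Possibly, but the program will follow the text.

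**The protocol leaves detail to the SAP.** It does. But SAP Section 13 exists to list changes, and it names only the treatment-emergent and baseline definitions.

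**Stronger readings to avoid.** A reader might infer that ORR will be inflated by next-line responses. The SAP ties best overall response to RECIST v1.1, and Protocol Appendix B does not reproduce that guideline's assessment window, so the documents do not settle this. A reader might also expect negative DOR values to be common. They need a first response after the switch in a patient alive at cutoff, and no frequency can be derived. The DOR paragraph also has a plain last-assessment rule that could not go negative; the sentence applying the rPFS rules, with the earliest-date note, overrides it.

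**Conclusion.** The defect holds on the text of Table 3. Censoring at a switch is conditional on surviving to cutoff, and neither row 5 nor the earliest-date note repairs it. The resulting estimate is biased downward and moves with cutoff. Under the main assumed rates and a cutoff close to the planned follow-up, the loss in 12-month rPFS is about 0.6-2.4 points. It is larger with earlier cutoffs, or with faster progression and heavier switching.

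A reader might infer that the rPFS results would be unusable. The documents do not support that: in a cohort of about 20, the exact 95% interval around 5/20 is 9-49%, far wider than the bias. The bias does not shrink with more patients, however, and it is avoidable. The negative DOR is a literal-text edge case and a secondary point. This should be corrected before analysis, but no stated decision rule turns on it.

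**What to change.** 1. In Table 3 row 3, delete the closing condition that the patient had not died by data cutoff. Every patient who starts subsequent therapy without prior progression is then censored at the last adequate pre-switch scan, whatever happens later.
2. Report the Protocol 9.5.5 definition as a sensitivity analysis: all progressions and deaths count, with no switching rule.
3. List the added switching rule in SAP Section 13.
4. State that response for ORR and DOR is derived only from scans up to the earlier of progression or start of subsequent anticancer therapy.

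The cost is SAP wording and one additional run, using therapy dates already collected. The small downside is that a response on next-line therapy no longer counts toward ORR.

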3.3.3 Study Duration

Patients will receive CORT125281 in combination with enzalutamide until reaching a protocol-defined event of disease progression, experiencing unmanageable toxicity, or until other treatment discontinuation criteria are met (Section 4.4.1). As per PCWG3, patients with an isolated PSA rise after an initial decline who show evidence of benefit should continue treatment until radiographic or clinical progression.

All patients will be followed for progression, information on subsequent anticancer therapies (start and end date and response) and survival.

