4.4.1 Patient Discontinuation of Study Treatment

Study treatment will be discontinued in any of the following occurrences:

- Progressive disease. If the patient is experiencing overall clinical benefit, the patient may be allowed to remain on the study. Both the Medical Monitor and the Investigator must agree that this is appropriate for the patient.
- Unmanageable toxicity.
- Request for early discontinuation or withdrawal of consent by the patient.
- The Investigator decides it is in the patient's best interest to discontinue treatment and/or participation in the study. Reasons may include the following:
 - The patient requires prohibited medications or initiates treatment with another drug for treating prostate cancer
 - The patient is not adherent to the protocol

If a patient discontinues CORT125281, enzalutamide will be continued per the guidelines provided in Section 5.7.1.1. If a patient discontinues enzalutamide, CORT125281 will also be discontinued.

Patients who discontinue study treatment for reasons other than withdrawal of consent (eg, AE, Investigator decision) will undergo a Post-Treatment/ EOT Visit and EOT +30 Days Visit, and will be followed for progression and survival.

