6.3.1 Physical Examination

Complete physical examinations and limited physical examinations will be performed at the time points noted in the SoA ([Appendix A](#)). At each visit after the first dose of CORT125281 and/or enzalutamide, the Investigator will perform an assessment focused on determining if the patient's disease has progressed, based on the standard of care at each site. The performance of the physical exam will be recorded in the appropriate eCRF by the Investigator (or designee).

Limited physical examinations will include assessment of skin, heart, lungs, and abdomen, in addition to symptom-directed assessment of other organ systems. Note: all clinically significant abnormalities occurring before signature of informed consent should be recorded in the Medical History and/or Oncology History section of the eCRF; all abnormalities occurring or worsening after signature of informed consent should be recorded in the AE section of the eCRF.

Weight will be reported at each visit where a physical examination is performed. Height will be recorded at Screening only. Height and weight (without shoes) will be measured using an appropriate measuring device. Historical patient information and/or patient reports should not be used for either measurement.

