4.2.2. Secondary Efficacy Endpoints

Efficacy will be assessed by evaluating the following endpoints:

- ORR: proportion of patients with an objective tumor response (either partial response [PR] or complete response [CR]) per investigator using RECIST v.1.1 in patients with measurable disease, including best radiographic response for soft tissue.
- A reduction in PSA level from baseline by 50% or more.
- Time to SSE defined as symptomatic fracture, radiation or surgery to bone, or spinal cord compression.
- rPFS: time from first dose of study treatment (exicorilant and/or enzalutamide) to the date when the first site of disease is found to progress on computed tomography (CT), magnetic resonance imaging (MRI), or radionuclide bone scan per the Prostate Cancer Working Group 3 (PCWG3) criteria, or death, whichever occurs first. Progression will be assessed by the investigator using RECIST v.1.1. The portion of patients who are progression-free at 4,6 and 12 months will also be summarized.
- DOR: time from the first occurrence of a documented objective tumor response (CR or PR) to the time of radiographic progression (per investigator using RECIST v.1.1) or death from any cause on study, whichever occurs first.
- Time to PSA progression, clinical progression (per investigator), and bone-disease progression.
- Overall survival: time from the first dose of exicorilant and/or enzalutamide to the date of death from any cause.

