8.1. Patient Disposition

Patient populations will be summarized for all patients enrolled and will include the number and percentage of patients in each analysis population.

All patients who discontinue with the study will be included in a data listing. For each treatment group and overall, disposition summaries will present the number of enrolled patients, number of patients completing the study per protocol, and the number of patients terminating the study early by primary reason for discontinuation. Primary reason for discontinuation of treatment, including any of the following, will be summarized:

- Disease progression.
- AE(s).
- Investigator decision.
- Patient withdrawal of consent for treatment.
- Patient withdrawal of consent from study.
- Protocol non-compliance.
- Patient Died
- Unknown / lost to follow-up
- Other

Counts and percentages of patients who complete the study and those who discontinue for any of the following reasons will also be calculated:

- Death
- Lost to follow-up
- Study Terminated by Sponsor
- Withdrawal of consent
- Other

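### SAP 9.1 times clinical progression by treatment stops for any disease progression, which does not match the Investigator-determined clinical progression endpoint

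*SAP*

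**What the plan says.** SAP 4.2.2 lists, among the secondary efficacy endpoints, "Time to PSA progression, clinical progression (per investigator), and bone-disease progression". Protocol 9.5.5 has the same entry: "Time to PSA progression, clinical progression (per Investigator), and bone disease progression". In both lists rPFS is a separate item. Neither document states what the Investigator must find in order to call progression clinical.

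SAP 9.1 makes clinical progression operational as an interval "defined as time from first dose of study treatment (exicorilant and/or enzalutamide) to date of treatment discontinuation due to disease progression". Its only censoring sentence is "Patients who are alive and progression-free will be censored at their end of study visit".

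Other provisions bear on how this works:

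- SAP 8.1 says "Primary reason for discontinuation of treatment, including any of the following, will be summarized". The list that follows has one undivided entry for disease progression.
- Protocol 3.3.3 says that patients with an isolated PSA rise after an initial decline who show benefit "should continue treatment until radiographic or clinical progression". It therefore names two different kinds of progression.
- Protocol 4.4.1 makes progressive disease a reason to stop treatment, but adds: "If the patient is experiencing overall clinical benefit, the patient may be allowed to remain on the study", subject to agreement of the Medical Monitor and the Investigator. The same section keeps patients under progression and survival follow-up after stops for reasons other than withdrawal of consent.
- SAP section 13 declares two changes from the protocol, to the treatment-emergent and baseline definitions. It does not mention clinical progression.

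**The concern.** The named endpoint is a clinical judgement by the Investigator. The analysed event is an administrative one: the day treatment stopped, with progression of any type as the reason. The two coincide only when treatment stops promptly because of clinical worsening. Otherwise the SAP rule can add events that are not clinical progression and leave out events that are.

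At stake is the meaning of one secondary result. Protocol 2.2 and SAP 3.2 ask for time to clinical progression, including the proportions progression-free at 4, 6 and 12 months. Under SAP 9.1 a reader of the report would see a curve and median headed clinical progression that describe something else, with no notice of the difference.

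**Working it through.** The documents give no figure for time to clinical progression, so there is nothing to reproduce. The main check sets the endpoint beside the rule for each course a patient can take.

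| Course | Endpoint per Protocol 9.5.5 and SAP 4.2.2 | SAP 9.1 as written |
|---|---|---|
| Worsens clinically and stops for it | Event | Event; the two agree |
| Stops on a scan finding alone, not clinically worse | No clinical event at that date | Event, because the reason is disease progression |
| Stops for toxicity, later progresses clinically | Event at the later date | No event. He is not progression-free, so the censoring sentence does not cover him either |
| Progresses clinically but stays on under Protocol 4.4.1 | Event at progression | Event at a later stop for progression; none if he stops for another reason or is still on treatment at the end |
| Dies without a progression stop | No rule given | No event; the censoring sentence covers only patients who are alive |

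Row 2 brings events forward or adds them. Rows 3 and 4 remove or delay them.

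**Illustration of direction only.** None of these inputs is in the documents. Assume a true median time to clinical progression of 8 months, independent exponential times, and treatment stopped at once on any progression. Let *f* be the share of progression stops that are radiographic, and *o* the share of all stops made for other reasons.

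*Radiographic stops alone (o = 0).* The clinical hazard is λ = ln 2/8 and the radiographic hazard is λf/(1 − f). They sum to λ/(1 − f), so the SAP 9.1 median is 8(1 − f):

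- f = 25%: 6.0 months
- f = 50%: 4.0 months
- f = 75%: 2.0 months

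The same share *f* of the counted events is not clinical progression.

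*Other stops alone (f = 0).* Because SAP 9.1 gives no rule, take one possible reading, in which these patients are carried event-free to 24 months. The counted events follow F(t) = (1 − o)[1 − exp(−λt/(1 − o))]. Setting F = 0.5 gives a median of −8(1 − o)·log2[1 − 0.5/(1 − o)]:

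- o = 20%: 8 × 0.8 × 1.415 = 9.1 months
- o = 40%: 8 × 0.6 × 2.585 = 12.4 months

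The share of clinical progressions within 24 months that is not counted is 1 − (1 − o)(1 − 2^(−3/(1 − o)))/(1 − 2^(−3)):

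- o = 20%: 1 − 0.741/0.875 = 15%
- o = 40%: 1 − 0.581/0.875 = 34%

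If they were censored at the stop instead, the median in this independent model would stay at 8 months. The unwritten rule therefore matters.

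*Both together.* The median in the second case is multiplied by (1 − f). With f = 25%, it is 0.75 × 9.1 = 6.8 months at o = 20%, below the true 8, and 0.75 × 12.4 = 9.3 months at o = 40%, above it. The sign depends on quantities that the documents do not give.

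**The case against.** The strongest reply is that the protocol never defines clinical progression beyond attributing it to the Investigator. Stopping treatment for progression is largely an Investigator decision, so SAP 9.1 fills a gap and does not override a definition. That stands in part: there is no protocol definition to violate. But the label has to mean something other than rPFS, PSA and bone progression, which are listed separately, and a rule that accepts any progression does not separate it from them. SAP 9.1 also fails to match the SAP's own section 4.2.2.

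Second, the eCRF is not among the documents and may record the type of progression. That is possible, but SAP 9.1 does not use such a split.

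Third, a cleaner date may not exist. Under Protocol 6.3.1, at visits after first dose, "the Investigator will perform an assessment focused on determining if" the disease has progressed, by each site's standard of care. This is not specific to clinical progression, and the section promises only that performance of the examination is recorded in the eCRF. Off treatment, Protocol 7.5 names radiographic progression, SSE and survival. This objection stands and shapes the fix.

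Several stronger readings are tempting and not supported:

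- *Toxicity drop-outs are counted as long-term successes.* SAP 9.1 is silent on those who later progress; it does not assign them to the event-free group.
- *Treated-through clinical progression is missed.* Protocol 4.4.1 requires overall clinical benefit, so the case is marginal, and it is mostly dated late.
- *The endpoint largely repeats rPFS.* That depends on an unknown radiographic share. rPFS also counts deaths, uses scan dates and has its own censoring table.
- *A particular bias in the median can be stated.* The inputs would be invented, and radiographic and clinical progression in one patient are unlikely to be independent.

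**Conclusion.** The mismatch is real. Read literally, SAP 9.1 counts imaging-only stops as clinical progression. It gives neither an event nor a censoring rule for clinical progression after a stop for another reason. It dates treated-through progression late.

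The net bias can be neither sized nor signed from the documents. The illustration shows only that the two main errors oppose each other; its 8-month median, independence and shares are assumptions. Two features of the illustration probably exaggerate the radiographic effect: positive correlation between the two kinds of progression would shrink it, and Protocol 4.4.1 lets some patients with scan-only progression continue.

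The consequence is limited to interpretation of one secondary, descriptive endpoint. Protocol 9.3 plans estimation only. The MTD rule in Protocol 5.6 and the PSA-based sample size in Protocol 9.4.2 do not use it. It would go too far to say that the secondary objective cannot be met, because a wording change or an honest label is enough. The change should still be made, since it alters what the report can claim.

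**What to change.** In SAP 9.1:

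1. Define the event as the first Investigator-determined clinical progression, using data already recorded, whether or not treatment stops on that date.
2. Do not count discontinuations that rest only on imaging or PSA.
3. Censor every patient without such an event at the last progression assessment. This also supplies the missing rule for patients who stop for other reasons and for deaths without clinical progression.

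If the collected data do not separate clinical from radiographic progression, or do not capture clinical progression off treatment, keep the present analysis under the label time to treatment discontinuation due to disease progression. Do not report it as clinical progression, and declare the departure in SAP section 13. In that case also state which drug's discontinuation is meant, because Protocol 5.7.1.1 lets some patients continue enzalutamide alone.

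The cost is SAP wording and some review of existing Investigator records. The first option may leave fewer clinical-progression events and so a less precise estimate.
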